4.4 REPORT OF DEVICE USAGE DATA

1. A report of PAP usage data (including average hours used per day, leak, pressure, and AHI) will be generated by the ResMed Data Analytics group at 90 days and 180 days and provided to the statistician for analysis.
2. A user-level analytics report of myAir engagement (including participants who registered for myAir and number of times they engaged with the app during the study) will be generated by the ResMed Data Analytics group at 90 days and 180 days and provided to the statistician for analysis.
3. A user-level analytics report of Restful engagement (including participants who registered for Restful and number of times they engaged with the app during the study) will be generated by Wellth at 90 days and 180 days and provided to the statistician for analysis.

4.5 STUDY FLOW

4.6 INFORMED CONSENT

IRB approved informed consent (21 CFR Part 50) will be obtained by the Investigator or delegated investigative staff. The Investigator or delegated staff will be responsible for confirming that each patient understands the nature, purpose, and risks associated with participating in this study.

The investigative site will have the option of remotely consenting patients. Patients will be securely emailed a patient-specific link to access and create a login with the EDC system (Medrio). This website will contain the informed consent form, HIPAA, instructions on how to have any questions answered, and a knowledge assessment. The same login will also be used later in the study to complete participant questionnaires.

Patients will be given sufficient time (either remotely or in clinic) to consider the study's implications, ask any questions, and get these questions answered before deciding whether to participate. If consented remotely, patients will be clearly provided with information on how to contact an appropriate investigative staff member for questions about the study. Patients will not be able to authorize consent until they have confirmed that they have no further questions about the study. A copy of the consent form will be emailed or given to each participant for their records so they are able to access the consent form at any time throughout the course of the study.

Participant consent for this protocol will be obtained prior to the initiation of any study procedures.

5 INTERVENTION

5.1 WELLTH APP (RESTFUL)

The intervention is the use of Restful, the Wellth self-management application. There is no clinical treatment intervention, as all participants will be receiving PAP therapy per standard of care.

Restful is a smartphone-based patient engagement tool that utilizes concepts from behavioral economics to help patients improve their adherence to therapy. The intervention includes:

Financial incentive:

The incentive is \$75, and is distributed as follows: Participants unlock \$5 after completing the app introduction/onboarding, and then \$10 for successful nights on days 1, 2, 3, 5, 8, 13, and 21. Successful nights are nights where therapy is used for ≥ 4 hours. Once money is "unlocked," the reward is always visible to the participant. However, participants only receive the financial reward if they unlock all \$75 by the end of the program. In between

“pay days,” participants receive positive reinforcement messages and visual cues but no financial reward is unlocked.

Recognizing that participants are likely to struggle initially, and that there are 9 days in which participants can afford to have non-adherent nights (i.e., $30 - 21 = 9$), the participants will be granted 9 hearts in the app. These hearts represent the “misses” available to them, and they will lose a heart each non-adherent night. The program will deliver a tailored intervention message of support or encouragement after every 2 lost hearts (e.g., remind participants how close they were to a successful night).

If the participant does not meet adherence in the first 5 weeks and/or they have lost 9 hearts, then they will get a second chance. The intervention will “reboot.” Participants will not be made aware of this opportunity at the outset.

Social incentive:

The social incentive will have two components: social currency and social support messages. Participants will have the opportunity to nominate a social support person during the Wellth onboarding process. This person will be contacted directly by Wellth via text message and provided with information that will explain their role in supporting the participant. The support person will be asked to provide social currency (described below) that they think will be meaningful to the participant, as well as some supportive messages. Over the course of the 90-day trial, Wellth will reach out to the support person to solicit additional currency and messages. If the support person is generally non-responsive, or if the participant does not nominate a social support person, then the participant will receive Wellth-designed content for the social currency and social support components.

- Social currency: Pictures and/or videos that are meaningful to the participant. Delivered to the participant when they hit a therapy usage streak of 3 days in a row ≥ 4 hours.
- Social support messages: Encouraging messages that are meaningful to the participant. Delivered to the participant at seemingly random intervals throughout the 90 days (i.e., via a rules-based delivery algorithm).

5.2 AIRVIEW

AirView is the HIPAA compliant web-based system that is routinely used for telemonitoring. The PAP device contains built in wireless connectivity which transmits data via a mobile network to a secure data center. Data is transmitted at the completion of each period of use (e.g. after each night of use). Data can then be accessed, via a login code, by the respiratory/sleep team to assess items such as device efficacy (residual AHI), mask leak, and usage hours.

AirView is compliant with HIPAA, EU 95/46/EC, and national privacy laws. Data are encrypted and all database accesses are logged and can be re-traced.

5.3 MYAIR

In addition to AirView, a patient-focused version of the data is available through the myAir app. The myAir app can be accessed via the participant's smartphone or computer and allows the participant to monitor their own treatment data. myAir also provides tips to the participant on things like coping with therapy, managing mask leaks, and adjusting comfort settings. These tips are personalized based on each individual's data. The myAir app is not mandatory in this trial, but participants' usage of myAir will be documented in both Group A and Group B.

5.4 CONTROL GROUP

The control group will be monitored and managed per the site's standard of care with the exception of completion of questionnaires at baseline and again at 90 days after enrollment.

6 DATA HANDLING AND RECORD KEEPING

6.1 CONFIDENTIALITY

Information about study participants will be kept confidential and managed according to the requirements of the Health Insurance Portability and Accountability Act of 1996 (HIPAA). Those regulations require a signed participant authorization informing the participant of the following:

- What protected health information (PHI) will be collected from participants in this study
- Who will have access to that information and why
- Who will use or disclose that information
- The rights of a research participant to revoke their authorization for use of their PHI
- All the institutes involved in the study to keep the medical information confidential and managed according to the requirements of the Health Insurance Portability and Accountability Act of 1996 (HIPAA)

6.2 SOURCE DOCUMENTS

Source data is all information, original records of clinical compliance records, observations, or other activities necessary for the reconstruction and evaluation of the study. Source data are contained in source documents. Examples of these original documents and data records include: participants' records, clinical and office charts, laboratory notes, memoranda, participants' diaries or evaluation checklists, recorded data from automated instruments, copies or transcriptions certified after verification as being accurate and complete, participant files, and records.

6.3 CASE REPORT FORMS

Participant data will be collected through use of a CRF and Participant Questionnaires (**Appendix A**). Objective usage data will be collected directly from AirView.

The clinical site will provide study data to the Sponsor by recording data in the Medrio EDC System (21 CFR Part 11 compliant).

6.4 RECORDS RETENTION

Records to be kept at the site. Records retention includes electronic as well as hard copy records for 5 (five) years after the final analysis is complete.

7 MONITORING

The site will utilize internal monitoring procedures to review the flow of the study and make sure that all procedures are being performed in a timely manner and the project meets the timelines.

8 ADVERSE EVENT REPORTING

For the purpose of this protocol, an adverse event is any deviation from baseline health in a participant that can be attributed to the device, disease, or study procedures required by this protocol.

A serious adverse event (SAE) is any event that is fatal or immediately life-threatening AND that requires a participant to be hospitalized or hospitalization is unduly prolonged because of potential disability or danger to life or because an intervention has been necessitated. This includes events that cause fetal distress, fetal death, congenital anomaly or malignancy or any permanently disabling event.

For the purposes of this protocol, 'serious' is defined as any significant adverse experience, including those which may be either life-threatening or involve permanent or long term injuries, but excluding injuries that are non-life-threatening and that are temporary and reasonably reversible.

As noted above, changes in a participant's health should be documented in the participant's record and an assessment should be made regarding association with the study device or procedure. If it is determined that the event can be attributed to the device or procedure required by the protocol, the investigator should obtain and document all the information required to document the event, including cause, treatment, and resolution. All adverse events must be followed until resolution or until a stable clinical endpoint is reached. If the event can be attributed to the device or study procedure, all required treatments and outcomes of the adverse event must be recorded on the CRFs.

Unanticipated adverse device effects are defined as any serious adverse effect on health or safety or any life-threatening problem or death caused by, or associated with, a device, if that effect, problem, or death was not previously identified in nature, severity, or degree of incidence in the investigational plan, or any other unanticipated serious problem associated with a device that relates to the rights, safety, or welfare of participants.

Under the requirements of the FDA's IDE Regulations, an investigator must submit to the manufacturer (or its designee) and to the reviewing Institutional Review Board any unanticipated adverse device effect occurring during the study as soon as possible, but in no event later than ten (10) working days after the investigator first learns of the effect.

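### Section 8 gives two conflicting definitions of seriousness: one requires hospitalization even for a fatal or life-threatening event, the other does not, and neither is said to govern

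*Combined protocol and SAP*

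**What the plan says.** All the relevant text is in Section 8 (Adverse Event Reporting).

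- **First paragraph, adverse event.** "any deviation from baseline health in a participant that can be attributed to the device, disease, or study procedures required by this protocol". Attribution to the disease is enough to qualify.
- **Second paragraph, SAE.** The event must be "any event that is fatal or immediately life-threatening AND that requires a participant to be hospitalized", or one where "hospitalization is unduly prolonged because of potential disability or danger to life or because an intervention has been necessitated". A list follows: "This includes events that cause fetal distress, fetal death, congenital anomaly or malignancy or any permanently disabling event". Fetal death is on the list; death of the participant is not.
- **Third paragraph, *serious*.** For this protocol the word "is defined as any significant adverse experience, including those which may be either life-threatening or involve permanent or long term injuries". The paragraph then carves out one group of events, namely by "excluding injuries that are non-life-threatening and that are temporary and reasonably reversible". Hospitalization is not mentioned.
- **Fifth paragraph, unanticipated adverse device effect.** This covers "any serious adverse effect on health or safety or any life-threatening problem or death caused by, or associated with, a device", if not already identified in the plan, and also other unanticipated serious problems associated with a device. The sixth paragraph requires these to be reported to the manufacturer and the IRB within ten working days. Section 8 sets no other deadline.

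No sentence ranks the second paragraph against the third or says that they serve different purposes.

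**The concern.** A site has to classify each event by one rule, and here it has two. The capitalised AND in the second paragraph makes hospitalization necessary even when the event is fatal. The third paragraph drops that condition. Two coordinators could classify the same out-of-hospital death differently, and each could cite Section 8.

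What is at stake is consistent safety classification. The word *serious* is also used inside the definition of an unanticipated adverse device effect. For a device effect that is neither fatal nor life-threatening, whether the ten-working-day clock starts can therefore depend on which meaning is taken. In a study expected to yield few events, a single misclassified death would be conspicuous.

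**Working it through.** No arithmetic applies. The check is a logical reading of the two definitions.

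**Step 1: the two ways to parse the SAE sentence.** Let F = fatal, L = immediately life-threatening, H = requires hospitalization, P = hospitalization unduly prolonged.

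- Parse 1: (F or L) and (H or P)
- Parse 2: [(F or L) and H] or P

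If H and P are both false, both parses are false whatever F and L are. Without a required or prolonged hospitalization, the sentence cannot be satisfied. Only the inclusion list can then bring an event in.

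**Step 2: apply both definitions to specific events.**

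| Event | SAE sentence, parse 1 / parse 2 | Inclusion list | Third paragraph | Do they agree? |
|---|---|---|---|---|
| Death, no hospitalization | No / No | Not listed | Serious, as a significant adverse experience | **No** |
| Life-threatening, no hospitalization | No / No | Not listed | Serious, named | **No** |
| Permanently disabling, not life-threatening, no hospitalization | No / No | Listed | Serious, as permanent injury | Yes, but only through the list |
| Long-term injury, not permanently disabling or life-threatening, no hospitalization | No / No | Not listed | Serious, as long-term injury | No (narrow remainder) |
| New admission for a temporary, reversible, non-life-threatening injury | No / No | Not listed | Excluded | Yes, not serious under either |
| Prolonged stay for such an injury because an intervention was needed | No / Yes | Not listed | Excluded | Depends on the parse |

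The first two rows do not depend on the parse, and they concern the gravest events.

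**Step 3: the SAE sentence against its own list.** The list is introduced as included in the class just defined. Yet a malignancy or a permanently disabling event need be neither fatal, nor immediately life-threatening, nor a cause of hospitalization. The list therefore contains events that fail the sentence it is meant to illustrate.

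**Step 4: what depends on each term.**

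- *SAE*: Section 8 attaches no deadline or separate report to it, and Section 3.9 (Data Analysis) plans no SAE table.
- *Serious*: it is used in the definition of an unanticipated adverse device effect. That definition names death and life-threatening problems separately, so those two do not depend on the word. Other device effects do.
- Section 9 (Expected Adverse Device Effects) lists no specific expected effect, so it gives the site little help in judging what was already identified.

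**The case against.** The strongest case on the other side is that little turns on the conflict. The working duties in Section 8 apply whether or not an event is called an SAE. Changes in health are documented, association is assessed, adverse events are followed to resolution or stability, and events attributed to the device or a study procedure go on the CRFs. A device-associated death would very probably count as unanticipated, because Section 9 lists no expected effects, and it would be reported within ten working days with no hospitalization condition. Sections 9 to 11 describe the study as very low or non-significant risk, and PAP therapy is standard of care in both arms.

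Most of this stands, and it rules out three stronger readings that a reader might infer.

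- *Out-of-hospital deaths are excluded from serious events and go unreported.* The exclusion follows only if the second paragraph is read alone. Taken whole, Section 8 contradicts itself on such a death, and the unanticipated-effect route remains open for device-associated deaths.
- *Long-term injuries without admission are generally lost.* The reference to permanently disabling events covers most of them. Only long-term injury short of permanent disability remains.
- *Every hospitalization ought to be serious, so a new admission for a minor event is misclassified.* Neither definition says this. For a new admission with a temporary, reversible, non-life-threatening injury, both give the same answer. Calling that an error would need a standard from outside the documents.

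Two things survive the objection. The unanticipated-effect route is limited to a device, whereas the adverse event definition also takes in events attributed to the disease. The introduction itself names cardiovascular disease and stroke as risks without sustained therapy. For a disease-attributed death outside hospital, seriousness rests entirely on the two conflicting definitions. In addition, the only deadline in the section uses the unsettled word.

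**Conclusion.** The concern holds as an internal contradiction. The SAE sentence is wrong as written: followed literally, it leaves a death or life-threatening event without hospitalization outside the SAE class, while the next paragraph calls the same event serious. This does not depend on how the sentence is parsed. It assumes only that the second and third paragraphs both apply, since nothing in the text sets either aside.

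The firm conflict covers one class of event, with a narrow remainder for long-term injury that is not permanently disabling. The effect is on event classification and on the meaning of *serious* in the unanticipated-effect definition. Expected counts are low on the plan's own description of risk. The documents give no event rate, so the number of affected events cannot be estimated. The primary endpoint, the secondary endpoints, the sample size of 300 and the efficacy analyses are unaffected. The correction is cheap and relevant to safety, and worth making for that reason.

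**What to change.** 1. Merge the second and third paragraphs of Section 8 into one governing definition of *serious*, and use it also in the unanticipated-effect paragraph.
2. Word it so that hospitalization is not a necessary condition for a fatal or life-threatening event. The third paragraph and the unanticipated-effect paragraph already imply this.
3. Make the inclusion list consistent with the definition, so that malignancy and permanently disabling events qualify in their own right and are not presented as examples of a sentence they may fail.
4. Have the sponsor state explicitly how hospitalization, new or prolonged, for a temporary, reversible, non-life-threatening event is classified. That decision is the sponsor's. A list that simply made every hospitalization serious would go beyond both definitions and reverse the third paragraph's exclusion.

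The cost is a protocol wording change and a matching CRF instruction. A few more events may be classed as SAEs. No change to the analysis or sample size follows.

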9 EXPECTED ADVERSE DEVICE EFFECTS

This study is considered to be of very low risk to the participant.

10 NON SIGNIFICANT RISK DETERMINATION

This study is considered non-significant risk (NSR) based on standard of care procedures being employed and a review of the Code of Federal Regulations for significant risk devices. As required by FDA, the IRB will review this study and determine if it concurs with the NSR designation.

11 RISK MITIGATION

This study is considered to be of very low risk to the patient due to the non-invasive nature of the procedures.

APPENDIX A: PARTICIPANT QUESTIONNAIRES

Note: Study is using electronic case report forms and patient reported outcomes. The attached PDF is an outline of all participant questionnaires available in EDC.

